3. OBJECTIVES

3.1. Main objectives

- Describe the population infected by COVID-19 with genitourinary tumors (urothelial cancer, prostate cancer, testicular cancer and renal cancer) treated in Spanish hospitals, know the clinical presentation, therapeutic evolution and prognosis of said intercurrent infectious process, as well as its possible relationship with different clinical and therapeutic factors.
- Assess the possible relationship of the different oncological treatments administered to these patients with the clinical evolution of COVID-19 infection, considering both patients who have undergone oncological treatment previously, during or after COVID-19 infection.
- To specifically evaluate the impact of COVID-19 infection on the toxicity of immunotherapy treatment (mainly pneumonitis) and the impact of immunotherapy on the evolution of the infectious condition in patients with tumors of genitourinary origin, in three different scenarios: during treatment, after treatment and in patients who are prescribed treatment after the infection has passed.
- Analysis of this same relationship in patients with genitourinary tumors and asymptomatic COVID-19 infection with positive Ab serologies (IgM and IgG).
- To evaluate in patients with Prostate Cancer (PCa) the impact of androgen deprivation therapy (ADT) and new antiandrogen agents (NAH) with or without corticosteroids on infection COVID-19.

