4.5. Study sample size

The inclusion of a total of 250 patients with genitourinary tumors presenting with COVID-19 infection is expected, sufficient to respond to the objectives set by the study.

Given the characteristics of the study, the total number of patients cannot be previously calculated accurately, although the inclusion of approximately 250 patients is expected. The planned analysis is the descriptive one of each of the variables. The qualitative variables will be compared with each other using the Chi-square test. Quantitative and qualitative analysis using Student's T analysis or ANOVA. If necessary, the corresponding non-parametric tests will be applied. Survival will be calculated using Kaplan-Meyer curves and curve comparison using Log-Rank.

The Statistical Package for the Social Sciences (SPSS) will be used for statistical analyses. Additional analyzes could be performed with other statistical analysis packages.

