5. VARIABLES

5.1. Study variables

A data collection notebook will be prepared in which the following variables will be collected for analysis:

Affiliation of the center:

- Hospital name
- Province
- Investigator's name
- Patient number

Patient characteristics:

- Age
- Sex
- Age
- Hospital center where the patient is recruited (in order to have epidemiological data on the pandemic that may be of interest)

Pathological history:

- Concomitant pathology (cardiac, pulmonary, renal, liver, Diabetes Mellitus, HIV, AI)
- Usual pharmacological treatment
- Smoking and alcohol habit

Tumor pathology:

- Tumor type, histology and stage (initial and at diagnosis of infection)
- Date of cancer diagnosis
- Active cancer treatment or follow-up
- Participation in clinical trial
- Type of treatment most recently received for the infection (Surgery; Radiotherapy; Chemotherapy: Drug, Immunotherapy, TD: Drug, HT: ADT alone or with Abiraterone, Enzalutamide, others)
- Treatment lines
- Start and last dose received of the most recent oncological treatment

For patients with prostate cancer:

- Local treatment and type (Surgery, Radiotherapy)
- Adjuvant ADT or advanced disease (start date)
- NAH (date and line of treatment)
- Associated corticosteroid treatment: Prednisone vs Dexamethasone (dose)

COVID-19 infection data:

- Confirmation date of COVID-19 infection
- PCR diagnostic test
- IgG or IgM serological diagnostic test
- Present symptoms

- Analytical alterations, lymphopenia, elevated CRP, high D-dimer.
- Thrombosis associated with COVID-19 infection
- Date of onset and disappearance of symptoms
- Days duration of fever and cough
- Radiological examination at the moment of greatest severity
- Complications of infection: presence of complications and/or hospital or ICU admission
- Admission date
- Date of most serious complication
- Treatments received for COVID-19
- Discharge status
- Fecha de alta / exit
- Negativization of the presence of viruses by PCR
- Negative PCR date

For patients who are receiving or have received immunotherapy treatments, additional information will be collected:

- Immunotherapy treatment line
- Start/end date of immunotherapy treatment
- Date of last dose received prior to COVID-19 infection
- Immunotherapy received as monotherapy or combination
- Type of immunotherapy
- Adverse effects

Prospective follow-up data (6 months from patient inclusion):

- Date of start or restart of oncological treatment after infection

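### Immunotherapy toxicity across the three timing scenarios has no risk window or exposure adjustment, so crude proportions would not be comparable

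*Combined protocol and SAP*

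**What the plan says.** The third main objective in section 3.1 (objective iii in the summary) concerns the "impact of COVID-19 infection on the toxicity of immunotherapy treatment (mainly pneumonitis") and, conversely, the effect of immunotherapy on the course of the infection. Both are to be evaluated "in three different scenarios: during treatment, after treatment and in patients who are prescribed treatment after the infection has passed".

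The statistical methods are all in section 4.5:
- "The planned analysis is the descriptive one of each of the variables".
- "The qualitative variables will be compared with each other using the Chi-square test".
- Student's t or ANOVA for quantitative variables, with non-parametric alternatives where needed.
- "Survival will be calculated using Kaplan-Meyer curves and curve comparison using Log-Rank".

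No section gives a toxicity window, a person-time rate, a time-to-toxicity analysis or any adjustment for exposure.

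Section 5.1 collects most of the dates that exposure time would need: "Start/end date of immunotherapy treatment", the last dose before infection, "Date of start or restart of oncological treatment after infection" and the last contact. Adverse effects appear as one item with no onset date. The immunotherapy module is for current or past recipients. The 6-month follow-up list has no adverse-effect item. Section 7 provides for serious adverse events and adverse drug reactions to be entered in the eCRF, without an analysis rule.

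**The concern.** The scenarios are defined by when immunotherapy was given relative to infection, so they also fix, at least in part, how much time on drug can be observed. A yes/no toxicity variable summarised as a proportion takes no account of that time. If the amounts differ, the proportions differ even when infection has no effect on toxicity.

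This bears on a main objective. Section 2.3 hopes the study will inform the choice of treatment in future pandemics. A low pneumonitis percentage in patients who start immunotherapy after infection could be taken as reassurance when it may only reflect a short observation period. The opposite error is possible under a different counting rule.

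**Working it through.** **1. The plan's own figure.** Section 4.5 states that "the total number of patients cannot be previously calculated accurately, although the inclusion of approximately 250 patients is expected". No alpha, power, toxicity rate, number on immunotherapy or number per scenario is given, so 250 cannot be reproduced and the precision for this objective cannot be derived. Every rate, duration and group size below is an assumption.

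**2. Observed time on drug.** For prospective patients who start after infection, time on drug within the follow-up is at most 6 months less the delay from inclusion to first dose. An assumed delay of 1 to 3 months leaves 6 − 1 = 5 to 6 − 3 = 3 months. Ongoing and completed courses have no such cap; 12 and 18 months are taken as examples.

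**3. Crude proportion under one common hazard.** P(t) = 1 − exp(−λt), with λ = −ln(1 − 0.05)/12 = 0.00427 per month, that is, 5% by 12 months in every scenario.

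| Months on drug | Expected crude proportion |
|---|---|
| 3 | 1.27% |
| 5 | 2.11% |
| 12 | 5.00% |
| 18 | 7.41% |

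The ratios run from 5.00/2.11 = 2.4 to 7.41/1.27 = 5.8. With 3% by 12 months they are 2.4 to 5.9, and with 10% they are 2.3 to 5.6. They depend on the assumed durations and the constant hazard, and hardly at all on the rate.

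**4. Direction.** Same formula, hazard 3% per month in all scenarios, three possible sets of counted months on drug:

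| Counted months (during / after / started after infection) | Expected proportions |
|---|---|
| 12 / 6 / 3 | 30.2% / 16.5% / 8.6% |
| 6 / 12 / 3 | 16.5% / 30.2% / 8.6% |
| 6 / 0 / 4, only events after infection counted | 16.5% / 0% / 11.3% |

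The 'after' group is second, highest or zero according to the durations and the counting rule. The plan does not choose between these.

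**5. If a chi-square test were applied (2 df, 5% level, simulated, no true difference in hazard).**
- At 5% by 12 months and 12/18/3 months on drug, it rejects in about 5%, 9% and 19% of runs with 15, 25 and 50 patients per scenario. With 12 months in every scenario the figures are about 2%, 4% and 4%. Expected events at 25 per scenario are only 25 × 0.0500 = 1.3, 25 × 0.0741 = 1.9 and 25 × 0.0127 = 0.3.
- At 10% by 12 months and 50 per scenario, it rejects in about 47%.
- At 1%, 3% and 6% per month (11.3%, 30.2% and 51.3% by 12 months) with 12/6/3 months and 25 per scenario, it rejects in 12.5%, 39.8% and 67.0%. With 6 months in every scenario it rejects in 3.5% to 5.1% over the rates and group sizes tried.

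Unequal time on drug is what raises the rejection rate. The rise is modest when events are rare and groups small, and large otherwise.

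**6. Can a rate per month on drug repair all three scenarios?** No. Patients in 'after' had stopped before infection. Counted from the infection date they have little or no time on drug, so the denominator is close to zero.

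**The case against.** Three stronger readings are tempting, and the documents do not support them.

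*That the plan prescribes a chi-square test of toxicity across the scenarios.* The objective speaks of evaluating in three scenarios, not of comparing them. The chi-square sentence is general, and the planned analysis is called descriptive. The comparison is an inference. The problem remains without a test, because three crude percentages side by side invite the same reading.

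*That patients treated after infection must look safest and 'after' patients most toxic.* This needs whole courses to be counted. The objective is the impact of infection, and events before infection cannot be part of that. If only later events count, 'after' may look least toxic. Nor do the documents give reasons for stopping, so any enrichment of 'after' by patients who stopped for toxicity is speculation.

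*That the distortion is 2.4- to 5.8-fold.* That range follows from an assumed constant hazard and assumed months on drug, none of which is in the documents. A hazard that falls over time would narrow it.

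It is also fair to object that the collected dates let time on drug be derived. That is true of the denominator. Section 5.1 lists no onset date for adverse effects, so events cannot be placed in a window, and this is more than an omission of analysis wording.

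**Conclusion.** The concern holds in a limited form. Section 4.5 sets neither a risk window nor an exposure adjustment for toxicity under the third main objective, and observed time on drug will generally differ between the scenarios. Crude proportions are therefore not comparable and can differ with no effect of COVID-19. The illustration (1.3% to 2.1% against 5.0% to 7.4%) shows that the difference need not be small, but it rests on a constant hazard of 5% by 12 months and on assumed durations. The documents fix neither the actual size nor the direction. A cross-scenario test is a natural use of the stated method, not a stated one.

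**What to change.** In section 4.5, for the toxicity part of this objective:
- Report the proportion with a first event within the same fixed window in each scenario, for example 90 days: from the infection date in 'during' and 'after', and from the first post-infection dose in the third.
- Allow for incomplete follow-up and for death, for example by cumulative incidence with death as a competing event.
- Keep events before infection separate.
- Add first events per patient-month on drug for 'during' and for starts after infection only. Report 'after' descriptively, because those patients have little or no time on drug after infection.
- Do not test crude whole-course proportions across scenarios.

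In section 5.1, add an onset date to the adverse-effects item. State that the immunotherapy module also covers patients who start immunotherapy after infection, including during the 6-month follow-up.

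The cost is one added eCRF field, the wider use of an existing module and a few derived variables. No patients or visits are added. The disadvantage is fewer countable events, so the estimates will be imprecise. A common window equalises observation time, not exposure: 'after' patients are mostly off drug during it, and the text should say so.

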3.2. Secondary objectives

- To evaluate the mortality associated with COVID-19 infection in the population with genitourinary tumors. Percentage of patients alive/dead at discharge.
- To evaluate the rate (percentage) of complications that have required hospital admission and/or ICU treatment.
- Describe the frequency of asymptomatic or minimally symptomatic COVID-19 infections. Percentage of asymptomatic patients or with mild symptoms included in the study.
- Evolution of the oncological disease. Impact/influence of COVID-19 infection on the effectiveness of oncological treatment. Data will be collected on delays/modifications in follow-up or oncological treatment regimens. The average delay time and the number of modifications will be evaluated. Likewise, it is expected to obtain data on time to progression and overall survival of cancer patients, which can be compared with the reference values for each type of tumor pathology.

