1.2. Methodological aspects

medical product of interest Not applicable
First ethics committee to evaluate the study: Autonomous CEIm of Galicia
Principal Investigators / Coordinators [REDACTED] [REDACTED]

[REDACTED]
 
[REDACTED]
 
[REDACTED]

Researcher/Coordinator Centers:
 
¹ Valencian Institute of Oncology
 
² San Carlos Clinical Hospital of Madrid
 
³ Puerta del Hierro-Majadahonda University Hospital
 
⁴ Lucus Augusti University Hospital, Lugo

Autonomous Communities of Researchers / Coordinators:
 
Valencian Community
 
Autonomous Community of Madrid
 
Galicia

Territorial scope:
 
National, Spain

Information source:
 
Medical records of the patients included after signing informed consent.
 
RETROSPECTIVE PART ONLY: medical records of patients included after signing informed consent or waiver thereof in the cases contemplated (see 6.3 Informed consent).

Type of study (according to the AEMPS classification):
 
EPA-AS

Tracking Type::
 
Ambispective (Prospective and retrospective). A 6-month follow-up is proposed for patients in the prospective part.

Total number of patients expected to include:
 
They are expected to include 250, sufficient to respond to the objectives set by the study.

Planned duration of the study:
 
Data collection 8 months. The estimated duration of the project is 12 to 18 months, depending on the patient inclusion rate.

Study duration for each participant:
 
No specific study visits will be carried out, other than obtaining informed consent in cases where it is required.

Main objectives:
 
a) Main objectives
 
i) Describe the population infected by COVID-19 with genitourinary tumors (urothelial cancer, prostate cancer, testicular cancer and renal cancer) treated in Spanish hospitals, know the clinical presentation, therapeutic evolution and

- prognosis of said intercurrent infectious process, as well as its possible relationship with different clinical and therapeutic factors.
- ii) Assess the possible relationship of the different oncological treatments administered to these patients with the clinical evolution of COVID-19 infection, considering both patients who have undergone oncological treatment previously, during or after COVID-19 infection.

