4.3. Inclusion criteria

- Patients ≥18 years old.
- Diagnosed with genitourinary cancer (urothelial, kidney, prostate and germ cell).
- COVID-19 infection prior to oncological treatment, during treatment or after treatment.
- COVID-19 infection must be confirmed by PCR or serology, regardless of whether or not the patient requires hospitalization due to the infection. Additionally, clinical and/or radiological determination must be available in those patients who present symptoms.

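### COVID-19 mortality is measured only as status at discharge, and retrospective patients have no listed dated status afterwards, which a fixed-day death rate and overall survival both need

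*Combined protocol and SAP*

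**What the plan says.** Section 3.2 states the mortality objective for the whole genitourinary tumour population. Its only measure is "Percentage of patients alive/dead at discharge". No number of days, time origin or denominator is attached to it, there or in the summary in section 1.2.

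Section 4.3 admits patients "regardless of whether or not the patient requires hospitalization due to the infection", and "COVID-19 infection must be confirmed by PCR or serology" is enough to qualify. Asymptomatic and mild infections are themselves a topic of sections 3.1 and 3.2, so never-admitted patients are expected.

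Section 5.1 lists the outcome items in two blocks:
- The general infection block has "Confirmation date of COVID-19 infection", the admission date, "Discharge status" and the half-translated "Fecha de alta / exit".
- Current status and the date of last contact appear only in a later block, headed as prospective follow-up over six months from inclusion.

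Section 1.2 agrees with that split: "A 6-month follow-up is proposed for patients in the prospective part".

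Section 3.2 also expects data on "time to progression and overall survival of cancer patients", under the objective on the course of the cancer. Section 4.5 plans Kaplan-Meier curves and the log-rank test for survival, with no time origin, horizon or censoring rule.

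**The concern.** A percentage taken at discharge has no common horizon: a short stay and a long one are each closed at their own end. A patient who goes home and dies soon after counts as alive. If discharge means leaving hospital, a never-admitted patient has no value. If it means the end of the infection episode, everyone has one. The plan does not say which.

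The more practical gap is in the data. A fixed-day death rate can be added later only if each patient's status and its date are on file. For prospective patients they are listed. For retrospective patients the last dated outcome listed is the discharge or exit date, so the analysis could not be repaired from the database, and overall survival in that part would have no follow-up after discharge. At stake is whether the study can answer its population mortality objective in full.

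**Working it through.** **The plan's own figure.** Section 4.5 expects about 250 patients and says the number could not be calculated accurately. No mortality rate, admitted share or precision target is given, so there is nothing to reproduce. The definition is checked by reading; the size can only be illustrated.

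**Tracing retrospective patients through section 5.1.**
- Dies during the admission: status at discharge is dead, and the exit date probably dates the death.
- Discharged alive, dies later: counts as alive in the section 3.2 percentage. No listed item holds the date of death. Under section 6.3 such a patient could even enter by the consent waiver, as someone who died before authorization, and still be alive at discharge in the data.
- Discharged alive and still alive: no listed item says until when.
- Never admitted: has a value on the end-of-episode reading, none on the hospital-discharge reading.

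**Size of the horizon effect.** All inputs are assumptions: admitted share h = 0.60, in-hospital mortality m = 0.30, share d of those discharged alive who die by the fixed day = 0.01, 0.03 or 0.05, and no deaths among never-admitted patients.

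Deaths at discharge over all included = h × m = 0.60 × 0.30 = 18.0%. In 250 patients that is 150 admitted, 45 deaths and 105 discharged alive.

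Increase by the fixed day, if all in-hospital deaths occur by then = h × (1 − m) × d:
- d = 0.01: 0.60 × 0.70 × 0.01 = 0.42 points, giving 18.4%
- d = 0.03: 0.60 × 0.70 × 0.03 = 1.26 points, giving 19.3%
- d = 0.05: 0.60 × 0.70 × 0.05 = 2.10 points, giving 20.1%

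For h = 0.40 the increases are 0.28, 0.84 and 1.40 points; for h = 0.80 they are 0.56, 1.68 and 2.80 points.

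**Direction.** If a share r of in-hospital deaths falls after the fixed day, the net change is h × [(1 − m) × d − m × r]. It is zero at r = (1 − m) × d / m = 0.70 × d / 0.30, which is 2.3%, 7.0% and 11.7% for the three values of d. Above that, the fixed-day figure is lower than the discharge figure.

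**Scale.** With 50 deaths in 250 (20%), the Wilson 95% interval is 15.5% to 25.4%. The shifts above are smaller than that sampling error.

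**The case against.** Status at discharge is a coherent descriptive measure for a secondary objective in a study whose planned analysis is descriptive, and arguably closer to deaths from the infection than all-cause death is. That stands, and is why the measure should be kept alongside the new one.

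Section 4.1 says the section 5 variables will be collected once patients are selected, without dividing them by study part. One could therefore hold that current status is meant for everyone. The block heading in 5.1 and the wording in 1.2 point the other way, so the gap stands as the plan is written, though it may be unintended.

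Centres will usually know who is alive: under section 6.3 retrospective survivors sign consent where possible, and patients covered by the waiver have died. This stands too, and it means the information is obtainable. It does not make it a listed, dated variable.

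A reader might infer more than the documents support:
- *Never-admitted patients have no mortality outcome.* The discharge items sit in the general infection block, so an end-of-episode reading is plausible. With the assumed inputs, 30% among admitted and 18.0% among all included are both valid once labelled, and both can be computed from listed items. The denominator is a matter of stating the definition.
- *The discharge figure must understate mortality.* The direction depends on how many in-hospital deaths fall after the chosen day.
- *Consent routes, late entry or serology-confirmed cases show a large bias in the mortality figure.* These concern who enters and when the clock starts, not the discharge measure. A fixed-day definition would not remove them, and they are not sized here.

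**Conclusion.** The point holds as a design weakness that should be corrected. The mortality objective in 3.2 is answered only in part, because its single measure has a patient-specific horizon, leaves out later deaths and does not say how it applies to never-admitted patients. As listed, retrospective patients lack the dated later status that a fixed-day estimate and the expected overall survival require.

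The numerical effect on the mortality percentage is probably modest: about 0.4 to 2.1 points over all included patients at 60% admitted and 30% in-hospital mortality. That rests wholly on assumed rates, on no deaths among never-admitted patients, and on all in-hospital deaths occurring by the fixed day; the sign can reverse if they do not. The stronger reason to act is that a status not collected for retrospective patients cannot be recovered at analysis. The documents do not support the claim that mortality cannot be computed at all.

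**What to change.** 1. In section 5.1, list current status and the date of last contact or death for retrospective patients too, taken from the medical record.
2. In section 3.2, add all-cause death by a fixed day from confirmed infection (for example day 30), with all included patients as the denominator. Use Kaplan-Meier where status at that day is unknown. Report it separately for the retrospective and prospective parts, and label the prospective figure as conditional on being alive to consent.
3. Keep status at discharge as a separate measure among admitted patients, and state what the discharge or exit date records, including for patients never admitted.
4. Show patients confirmed by serology alone separately, because their confirmation date may fall after the acute illness and is an uncertain time origin.

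The cost is a short definition and two record-based items; confirmation date, test type, admission date and discharge data are already listed, and Kaplan-Meier is already planned. The drawbacks are that all-cause death will include some tumour deaths, and that separate reporting gives smaller groups and wider intervals.

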4. STUDY METHODOLOGY

4.1. Study type and design

This is a national multicenter, observational, retrospective and prospective post-licensure (EPA-AS) study that will include patients with genitourinary tumors presenting with COVID-19 infection.

The study will be carried out in Spanish hospital centers, with principal investigators belonging to the medical oncology services of the SOGUG group (Spanish Genitourinary Oncology Group), who will act as sponsor. Once the patients are selected, the variables described in section 5 of this protocol will be collected and studied.

The study will use data obtained from the patient's medical history, with no plans to use other sources.

The assignment of a patient to a specific therapeutic strategy has already been decided in advance by the usual clinical practice of medicine; The decision to prescribe a specific treatment is clearly dissociated from the decision to include a patient in the study. No intervention, whether diagnostic or follow-up, will be applied to patients other than standard clinical practice. Epidemiological methods will be used to analyze the data collected.

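### Section 3.2 promises an average delay, but delay is undefined and section 5.1 lists no planned date or dosing interval against which to measure it

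*Combined protocol and SAP*

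**What the plan says.** The fourth secondary objective in section 3.2 (repeated in the summary, section 1.2) concerns the course of the cancer and the influence of COVID-19 on its treatment. It says "Data will be collected on delays/modifications in follow-up or oncological treatment regimens" and then "The average delay time and the number of modifications will be evaluated". It gives no definition, reference date or unit for delay.

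Section 4.1 ties the data to section 5: "Once the patients are selected, the variables described in section 5 of this protocol will be collected and studied". The relevant items in section 5.1 are:

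- For all treatments: "Start and last dose received of the most recent oncological treatment".
- For immunotherapy: "Date of last dose received prior to COVID-19 infection".
- For the infection: "Confirmation date of COVID-19 infection".
- In the prospective follow-up block: "Date of start or restart of oncological treatment after infection", a field for change or suspension of treatment, and the surgery date for neoadjuvant patients.

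The treatment type is recorded, with the drug for several classes. Section 4.5 plans descriptive statistics and general tests. It has no rule for delay and no breakdown of delay by regimen.

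**The concern.** A delay is the actual date minus the date on which the event was due. The list holds the actual date but not the due date. Any delay computed from it must start from another event, and that gap then includes time during which no treatment was due. The amount of such time depends on the schedule: almost none for a daily oral drug, weeks for a cyclic regimen. The study pools chemotherapy, immunotherapy, targeted and hormonal treatment, so the average can shift with the case mix while the disruption due to COVID-19 stays the same. Two analysts who chose different starting events would also report different averages from the same data.

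Two further parts of the objective lack data. Section 4.3 admits patients infected before oncological treatment; they have no last dose, and no planned start date is listed for them. Delay in follow-up has no variable, because neither a planned nor an actual date of a follow-up visit or imaging is listed.

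**Working it through.** The plan gives no figure or formula for delay, so there is nothing to reproduce. The check is what the listed dates can yield.

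**Inputs.** From section 5.1: last dose, infection confirmation and restart dates. Assumed, because the documents give none: dosing interval *i* of 1, 14, 21, 28, 42 or 90 days; true delay *d* of 0 or 14 days, the same in every patient; infection confirmed at a uniformly distributed point in the cycle.

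**Formulas.**
- Last dose to restart = *i* + *d*.
- Confirmation to restart = remaining part of the interval + *d*, on average *i*/2 + *d*.

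| Interval *i* | Last dose to restart, *d* = 0 | Confirmation to restart, *d* = 0 | Last dose to restart, *d* = 14 | Confirmation to restart, *d* = 14 |
|---|---|---|---|---|
| 1 | 1 | 0.5 | 15 | 14.5 |
| 14 | 14 | 7 | 28 | 21 |
| 21 | 21 | 10.5 | 35 | 24.5 |
| 28 | 28 | 14 | 42 | 28 |
| 42 | 42 | 21 | 56 | 35 |
| 90 | 90 | 45 | 104 | 59 |

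**Pooled means, true delay 14 days in everyone.**

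| Mix | From last dose | Ratio to 14 | From confirmation | Ratio to 14 |
|---|---|---|---|---|
| Daily : 21-day, 80:20 | 0.8×15 + 0.2×35 = 19 | 1.4 | 0.8×14.5 + 0.2×24.5 = 16.5 | 1.2 |
| Daily : 21-day, 50:50 | 25 | 1.8 | 19.5 | 1.4 |
| Daily : 21-day, 20:80 | 0.2×15 + 0.8×35 = 31 | 2.2 | 0.2×14.5 + 0.8×24.5 = 22.5 | 1.6 |
| 21-day : 90-day, 50:50 | (35 + 104)/2 = 69.5 | 5.0 | (24.5 + 59)/2 = 41.75 | 3.0 |

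For the three daily/21-day mixes with no true delay, subtract 14: 5, 11 and 17 days from last dose, or 2.5, 5.5 and 8.5 from confirmation.

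**Sensitivity to the equal-delay assumption.** Suppose instead that treatment resumes on the scheduled date or 14 days after confirmation, whichever is later. The true mean delay then falls as the interval lengthens, because part of the 14 days is absorbed by time when nothing was due. For *i* of at least 14 days it equals 14²/(2*i*): 7.0, 4.7, 3.5 and 2.3 days at 14, 21, 28 and 42 days. The gap from last dose rises over the same intervals (21.0, 25.7, 31.5, 44.3), and the gap from confirmation rises from 14.0 to 23.3. In that case the listed gaps rank the regimens in the opposite order to the true delay.

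**With a planned date.** Actual minus planned date returns *d* in every row of the first table, whatever the interval or mix.

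**The case against.** The strongest reply is that the plan prescribes no faulty calculation. A reader might infer that the normal dosing interval will be counted as COVID-19 delay. The documents do not support that, because no formula is stated; the overstatement is a risk that follows from the listed fields. A reader might also infer that last dose to restart is the only gap available. It is not: the confirmation date is listed too, and it roughly halves the excess. Dates of symptom resolution, discharge and negative PCR are listed as well, but none of them is a planned treatment date.

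The drug or treatment type is recorded, so an analyst could add a typical interval to the last dose. This would help for drug treatment. It is not planned, a drug name does not fix the schedule actually prescribed, and it does nothing for surgery or a first treatment start.

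The zero-delay figures also depend on how sites complete the restart field. If they fill it only after an interruption, a patient who missed nothing contributes no value. That objection stands, but it leaves the 14-day figures for interrupted patients unchanged.

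Finally, this is one descriptive component of the fourth secondary objective. No main objective, mortality or admission measure depends on it, and no comparison of delay between tumour types is specified. That stands and limits the severity.

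**Conclusion.** The concern holds as a gap in the data to be collected as well as in the definition. The listed variables do not allow an unbiased delay to be computed directly, and either readily available gap contains all or about half of the normal interval. Under the assumed intervals and a true 14-day delay, the daily/21-day mixes overstate the mean about 1.2 to 2.2 times, depending on the mix and the starting event. The fivefold figure should not be read as the expected error: it needs an even 21-day/90-day mix, with no daily oral drugs and measurement from last dose, and the documents support neither that mix nor those intervals. For daily oral drugs alone the excess is about a day or less, so the average is affected by the drug mix without being determined by it. A bias in comparisons between tumour types would be possible only if such comparisons were added. Severity: should-fix.

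**What to change.** 1. Add to section 5.1 the date on which the next dose, treatment start or surgery was planned when infection was confirmed. If it is not charted, record the regimen interval and take the planned date as last dose plus interval.
2. In section 3.2, define delay as actual minus planned date. Report it by treatment class, with the number of patients who never restarted and the number of planned dates that were derived or missing.
3. Either add the planned and actual dates of the first follow-up visit or imaging after infection, or delete follow-up from the delay objective.

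The cost is a few date fields abstracted from the same medical records and a short definition. No patient's care changes and no visit is added. The downside is that some planned dates will be missing or derived, especially in the retrospective part, which is why their number should be reported. The change is cheapest before data entry; later, charts at up to 32 centres would have to be reopened.
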